Baseline electrocardiogram and 24-hour Holter monitoring demonstrated substantial conduction and rhythm abnormalities, including bundle branch blocks and atrial fibrillation/flutter. There were no clinically relevant changes over time in these assessments, with perhaps slight improvement in cardiac autonomic function as demonstrated by improved heart rate variability indices.

Over the 12 months of tafamidis treatment, the patients' quality of life was maintained as was their functional status, as assessed by the SF-36, and KCCQ and PGA, respectively. The majority of these results were also better when compared with TRACS.

Seven patients participated in both TRACS (median follow up 12.5 months, with range of 6-26 months) and in Study Fx1B-201. All seven patients completed 12 months of treatment with tafamidis. However, given the small number of patients, it is difficult to assess whether disease progression was different during treatment with tafamidis as compared to standard of care in TRACS. The rate of cardiovascular hospitalization was similar between the two 12-month periods, with some evidence of stabilized cardiac function (ejection fraction and fractional shortening) observed following treatment with tafamidis.

Overall, tafamidis was effective in achieving and maintaining TTR stabilization in both wild-type and V122I patients and showed an apparent stabilization of the progression of cardiac disease.

The safety data described reflect exposure of 127 TTR-FAP patients to 20 mg of tafamidis administered daily for an average of 538 days (ranging from 15 to 994 days). The population was composed of adult patients diagnosed with symptomatic TTR-FAP, with a mean age of approximately 44 years; approximately half of the patients were female, and approximately 90% of the patients were Caucasian. Note that primary evidence of safety and efficacy was obtained from a placebo-controlled 18-month study in patients with TTR-FAP.

Table 1 provides a summary of the most common treatment emergent adverse events (TEAEs) ($\geq 5\%$ in tafamidis treatment group) during study Study Fx-005.

Table 1. Summary of Most Common ($\geq 5\%$ in Tafamidis Treatment Group) Treatment-Emergent Adverse Events Sorted in Descending Incidence in the Overall Tafamidis Group – TTR-FAP Patients, Study Fx-005 (Safety Population)

MedDRA Preferred Term	Number (%) of Subjects	
	Tafamidis 20 mg N=65	Placebo N=63
Number of patients with at least 1 AE	60 (92.3)	61 (96.8)

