**Cardiac Measures:** Changes from baseline (defined as the last evaluation prior to the first dose of study drug) will be summarized for each of the cardiac parameters listed above by visit. Clinically significant changes in ECG measures (as indicated by the items in [Section 6.2, #6](#), item h through m) at any point during the study will be summarized.

Pacemaker and defibrillator insertion procedures will be identified through a programmatic search of potentially related terms in the clinical database coupled with a manual review by Pfizer Clinical.

The following MedDRA Lower Level Terms (codes) will be applied to the Medical History, Adverse Events, and Investigator Comments to identify potential procedures in the clinical

database: CARDIOVERTER PLACEMENT (10053015), INSERTION OF IMPLANTABLE CARDIOVERTER DEVICE (10052044), CARDIAC PACEMAKER INSERTION (10007598), PACEMAKER INSERTION (CARDIAC) (10033352), DEFIBRILLATOR/PACEMAKER INSERTION (10069072), IMPLANTABLE DEFIBRILLATOR INSERTION (10049442).

The following terms will also be searched to identify potential associated procedures collected in the Investigator Comments CRF: pacemaker, implantable cardiac device, ICD, AICD, cardioversion, cardioverter, defibrillator, ventricular fibrillation, ventricular tachycardia.

Final search criteria and categorization of pacemaker and defibrillator will be based on the results of the clinical review and will be described in the programming plan prior to database finalization.

The number and percentage of subjects with pacemaker or defibrillator insertion procedures (defined above) will be summarized by category and for overall at baseline of Fx1B-201, the number and percentage of subjects who have such devices implanted during the course of Fx1B-201 and during the course of B3461026 (Fx1B-303), respectively.

**Vital signs:** Will be summarized using descriptive statistics, to include: values at each visit, change from baseline to each visit and a categorization of clinically significant changes.

Significant changes from baseline are defined as follows:

- Systolic Blood Pressure (mmHg) Decrease (Change  $\leq$  -20, or Value < 90)
- Systolic Blood Pressure (mmHg) Increase (Change  $\geq$  20, or Value > 180)
- Diastolic Blood Pressure (mmHg) Decrease (Change  $\leq$  -15, or Value < 50)
- Diastolic Blood Pressure (mmHg) Increase (Change  $\geq$  15, or Value > 105)
- Heart Rate (bpm) Decrease (Change  $\leq$  -15, or Value < 50)

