- Heart Rate (bpm) Increase (Change  $\geq$  15, or Value > 120)
- Weight (kg) Decrease (Change  $\leq$  -7%)
- Weight (kg) Increase (Change  $\geq$  7%)

Orthostatic hypotension is present under any of the following conditions:

- (Lying Systolic Blood Pressure - Standing Systolic Blood Pressure)  $\geq$  20 mmHg, or
- (Lying Diastolic Blood Pressure - Standing Diastolic Blood Pressure)  $\geq$  10 mmHg, or
- (Standing Pulse - Lying Pulse)  $>$  20 bpm along with (Standing Pulse or Lying Pulse  $>$  100bpm)

If pulse is missing at any visit, then evaluate orthostatic hypotension using only blood pressure measures.

**Concomitant medications:** will be summarized.

**Physical Examination and Medical History:** Results will be summarized and listed.

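### SBP, DBP and heart-rate flags for significant change from baseline can be met by an absolute value alone, so subjects already beyond a limit at baseline are counted as having changed

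*SAP*

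**What the plan says.** SAP 8.3, under Vital signs, promises a categorization of clinically significant changes and opens the list with "Significant changes from baseline are defined as follows". Six of the eight criteria join a change condition and a value condition with 'or':

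- SBP decrease: change of at least 20 downward, or value below 90; after its minus sign the criterion reads "20, or Value < 90".
- SBP increase: "20, or Value > 180".
- DBP decrease and heart-rate decrease, identical after the minus sign: "15, or Value < 50".
- DBP increase: "15, or Value > 105".
- Heart-rate increase: "15, or Value > 120".

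The other two criteria, weight decrease and increase, use a 7% change and no absolute value.

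Under Cardiac Measures, the same section refers to "Clinically significant changes in ECG measures (as indicated by the items in" SAP 6.2, item 6, h to m, and counts any occurrence during the study. Items h, i and j are QTc above 450, 480 and 500 msec. Items k, l and m are QTc changes of 30 to under 60, at least 60, and at least 90 msec.

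Change is measured from the Fx1B-201 baseline (SAP 8.1.1). The shift tables named in SAP 8.1.2 and 8.2 are for the Patient Global Assessment, NYHA class and 6-minute walk test.

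**The concern.** A row called a significant decrease or increase from baseline should count subjects who moved. Here, a subject who entered beyond the limit is counted at every visit where the value is still beyond it, whether it is unchanged or moving back toward the limit. The reader cannot undo this from the table, because the value and change conditions share one row.

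This matters more than usual here. There is no control group (Protocol 3.1), so baseline is the only reference for what treatment added. At most 35 subjects are expected (Protocol 9.1), so each miscounted subject moves a percentage by 1/35 = 2.9 points. Interim results may go to scientific meetings and regulators (SAP 3.2). Pre-existing ECG abnormality is documented for the parent study: "Baseline electrocardiogram and 24-hour Holter monitoring demonstrated substantial conduction and rhythm abnormalities" (Protocol 1.2.4). Baseline QTc above a limit is therefore plausible, although no QTc values are given.

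**Working it through.** The plan states no figure to reproduce. The check applies the rules literally to hypothetical pairs of baseline and visit values, then estimates the size under stated assumptions.

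**Step 1: rules applied as written.** With c = visit value minus baseline, SBP Decrease is c ≤ −20 or value < 90, and SBP Increase is c ≥ 20 or value > 180. DBP uses 15, 50 and 105; heart rate uses 15, 50 and 120. The amended rule counts the value condition only if baseline had not already met the same limit.

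| Pair | c | SAP rule | Amended rule |
|---|---|---|---|
| SBP 85 to 85 | 0 | Decrease | none |
| SBP 84 to 88 | +4 | Decrease | none |
| SBP 190 to 182 | −8 | Increase | none |
| SBP 205 to 182 | −23 | Decrease and Increase | Decrease |
| DBP 46 to 49 | +3 | Decrease | none |
| DBP 112 to 106 | −6 | Increase | none |
| HR 45 to 48 | +3 | Decrease | none |
| HR 130 to 122 | −8 | Increase | none |
| SBP 92 to 88 | −4 | Decrease | Decrease |
| QTc 505 to 505 | 0 | h, i, j | none |
| QTc 470 to 455 | −15 | h | none |
| QTc 440 to 460 | +20 | h | h |

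Six of eight vital-sign criteria and three of six QTc criteria can be met with no change, or with movement back toward the limit. Genuine new crossings (SBP 92 to 88, QTc 440 to 460) survive the amendment.

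**Step 2: size for SBP Decrease.** All inputs are assumptions: stable subjects with no true change, mean 115, between-subject SD 15, within-subject SD 6 or 10, and 8 or 20 visits. Protocol 6.2.2 lists 19 six-monthly visits, so 20 is the full schedule with the end-of-study visit. A subject counts if flagged at any visit. Simulation with 200,000 subjects per setting:

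| Within-subject SD, visits | SAP rule | Amended rule | Difference | × 35 |
|---|---|---|---|---|
| 6, 8 | 18.4% | 12.9% | 5.5 points | 1.9 |
| 6, 20 | 25.9% | 20.2% | 5.7 points | 2.0 |
| 10, 8 | 46.0% | 39.5% | 6.5 points | 2.3 |
| 10, 20 | 61.6% | 54.8% | 6.8 points | 2.4 |

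**Step 3: cross-check without simulation.** Only subjects with baseline below 90 can be added by the defect. Their share is Φ((90 − 115)/√(15² + 6²)) = Φ(−1.55) = 6.1%, or Φ((90 − 115)/√(15² + 10²)) = Φ(−1.39) = 8.3%. The differences of 5.5 to 6.8 points lie within these ceilings.

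**Step 4: effect on a reported percentage.** Suppose no subject newly changed but 1, 3 or 5 of 35 were beyond a limit at baseline (assumed counts). With the exact intervals of SAP 8.1.2, the table would report 2.9% (95% CI 0.1 to 14.9), 8.6% (1.8 to 23.1) or 14.3% (4.8 to 30.3).

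**The case against.** The strongest reply has four parts.

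- **Limited consequence.** The study is descriptive with no hypotheses (SAP 4.1), and no decision rule uses these flags. Vital-sign values and changes are also summarized by visit, and individual listings are planned (Protocol Summary, Statistical Methods), so a mislabelled flag can be traced. This stands and limits the severity. It does not repair the table: by-visit summaries do not show who was beyond a limit at baseline, and no shift table is committed for vital signs or QTc. The phrase introducing the shift tables in SAP 8.1.2 is open-ended, but neither is named.
- **QTc.** Items h to j and k to m are separate rows, and baseline values are to be summarized (SAP 6.7). A QTc going from 470 to 455 appears in row h and in none of the change rows. This largely stands. What remains is the label and the missing split by baseline status.
- **Noise, not the defect.** A reader might take the 18 to 62% of stable subjects flagged in Step 2 as the size of the error. It is not: 13 to 55% remain after the amendment, through the change condition or through new crossings.
- **Accumulation.** A reader might infer that vital-sign flags build up over 10 years. The SAP states an any-time count for ECG only and gives no tally rule for vital signs, so the any-visit figures rest on an assumption.

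**Conclusion.** The point holds for the six SBP, DBP and heart-rate criteria, on the wording alone and with no numerical assumption: the stated rule counts non-changes as changes. Weight and QTc items k to m are not affected. QTc items h to j have a labelling fault and lack a baseline split, but they do not mix value with change.

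The size is modest and uncertain. Under the assumed SBP inputs and an any-visit tally, the defect adds about 5 to 7 points, or roughly 2 of 35 subjects. The documents give no vital-sign or QTc distribution and no count of subjects beyond any limit at baseline, so they support no firm estimate. In particular, they do not support reading the future QTc tables as showing spurious drug effects of any stated size.

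This should be corrected, but it threatens no test or decision.

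**What to change.** In SAP 8.3:

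1. For SBP, DBP and heart rate, count the value condition as a change only when the baseline value did not already meet the same limit and the visit value moved in the named direction. Use the Fx1B-201 baseline already used for change.
2. Report the value condition and the change condition as separate rows.
3. Label QTc items h to j as absolute values, and show each by baseline status: new, or already beyond the limit at baseline.

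Do not require both conditions together. That would drop a fall in SBP from 150 to 95 (change −55, value not below 90) and one from 105 to 88 (change −17), a loss of sensitivity that a single-arm safety study need not accept. Both stay flagged under the rule above.

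The cost is SAP wording and programming on data already collected. The downside is slightly fewer flags and a few more table rows.

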For both wild-type and variant ATTR-CM, TTR amyloid fibrils are deposited in the myocardial interstitium, causing an increase in ventricular wall thickness, inducing myocardial damage and affecting myocardial function. Clinical symptoms include dyspnea on exertion, shortness of breath, orthostatic hypotension, syncope, and atrial fibrillation. Electrocardiogram findings demonstrate low voltage [14], particularly in light of the markedly thickened ventricular walls (median wall thickness of 17 mm [14]) demonstrated by echocardiogram. Amino-terminal B-type natriuretic peptide (NT-Pro-BNP), a serum marker of cardiac wall stress, is elevated in this population [15].

Current treatment is symptomatic, with careful fluid management and management of arrhythmias the mainstay. Median survival is approximately 60 months [14, 15], with 42% of patients dying from a cardiac cause [16]. Combined heart and liver transplantation is a current treatment option, however limited organ availability and significant patient comorbidity limit transplant as a treatment option.

The natural history of TTR-CM was studied in the Transthyretin Amyloidosis Cardiac Study (TRACS), in a cohort of patients followed longitudinally for 24 months. Using a variety of cardiovascular monitoring examinations (e.g., electrocardiograms [ECG], echocardiography, cardiac magnetic resonance imaging [MRI], exercise tolerance testing), the study evaluated how the disease affects patients over time. This information will be utilized in two ways: (1) to better define the natural course of the disease; and (2) more importantly, to better understand how to measure the effectiveness of future treatments by identifying endpoints that are well-correlated with disease progression/regression and to support the selection of endpoints to be used in clinical trials.

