7.2. Physical Examinations and Vital Signs

A complete physical examination, weight and vital signs, will be performed at the end of study visit, including assessment of the following body systems:

General appearance	Endocrine
Head and neck	Cardiovascular
Eyes	Abdomen
Ears	Skin
Nose	Musculoskeletal
Throat	Neurological
Respiratory	Immunologic/Allergies
Genitourinary	Hematologic/Lymphatic

During the trial, abbreviated physical examinations, including weight and vital signs, will assess general appearance, cardiovascular, respiratory, and gastrointestinal systems at each 6-month clinic visit.

Vital signs to be measured include lying and standing systolic and diastolic blood pressure (mmHg), lying and standing pulse (beats per minute), oral temperature (°C), and respiration rate (breaths/minute).

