9.1. Sample Size Determination

There is no formal sample size calculation for this protocol. Subjects who completed Protocol Fx1B-201 are eligible; up to 35 subjects are expected to enroll in Protocol Fx1B-303.

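### The SAP's orthostatic hypotension rule can be met on pulse criteria with no fall in blood pressure, so the count can include subjects whose pressure is unchanged or rises on standing

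*SAP*

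**What the plan says.** SAP Section 8.3, under Vital signs, gives the rule: "Orthostatic hypotension is present under any of the following conditions". The three conditions are:

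- Systolic: "Lying Systolic Blood Pressure - Standing Systolic Blood Pressure" of at least 20 mmHg.
- Diastolic: "Lying Diastolic Blood Pressure - Standing Diastolic Blood Pressure" of at least 10 mmHg.
- Pulse: standing minus lying pulse greater than "20 bpm along with (Standing Pulse or Lying Pulse" above 100 bpm).

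They are joined by or. A further sentence deals with incomplete data: "If pulse is missing at any visit, then evaluate orthostatic hypotension using only blood pressure measures".

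Protocol Section 7.2 supplies the measurements: "Vital signs to be measured include lying and standing systolic and diastolic blood pressure (mmHg), lying and standing pulse (beats per minute"). Protocol Section 1.2 names the condition as part of the disease picture: "Clinical symptoms include dyspnea on exertion, shortness of breath, orthostatic hypotension, syncope, and atrial fibrillation".

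Nothing else in either document qualifies the rule. The amendment table in SAP Section 1 records only that a definition was added. Protocol Section 2.2 lists vital signs as a safety endpoint without defining orthostatic hypotension, and SAP Section 6.2 mentions neither.

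**The concern.** The label says hypotension, but one of the three ways to earn it does not look at pressure. A marked rise in pulse on standing may be worth reporting, but it is a different finding from a fall in pressure. Pooling the two under one name means a reader of the safety summary cannot tell how many subjects actually had a fall.

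Two features make this more than a matter of naming. The study has no control group (Protocol Section 3.1), so no second arm carries the same over-count for a reader to compare against. Also, the definition depends on what was recorded: at a visit without pulse, the rule falls back to pressure alone, so identical pressures can be classed differently. Part of any apparent change over time could then reflect how completely pulse was recorded.

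What is at stake is the accuracy of one safety count, for a condition that the protocol itself lists as a feature of the disease.

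**Working it through.** The plan states no rate or count for orthostatic hypotension, so there is no figure to reproduce. The check applies the rule as written to individual readings.

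**Inputs.** The conditions and the or between them come from SAP Section 8.3. The expected sample size comes from Protocol Section 9.1: "up to 35 subjects are expected to enroll in Protocol Fx1B-303". The readings below are illustrative.

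**Rule as written.** Let L be lying and S standing.

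- A: L systolic − S systolic ≥ 20
- B: L diastolic − S diastolic ≥ 10
- C: (S pulse − L pulse > 20) and (S pulse > 100 or L pulse > 100)
- SAP rule: A or B or C. When pulse is missing: A or B.

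**A simplification of C.** If the pulse rises by more than 20 and the lying pulse is above 100, the standing pulse is above 120. The lying-pulse alternative therefore never changes the result, and C reduces to a rise above 20 bpm with a standing pulse above 100 bpm.

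**Results.**

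| Lying to standing pressure | Lying to standing pulse | A | B | C | SAP rule | Pressure only |
|---|---|---|---|---|---|---|
| 120/70 to 124/74 | 82 to 104 (rise 22) | no | no | yes | present | absent |
| 120/70 to 120/70 | 80 to 105 (rise 25) | no | no | yes | present | absent |
| 120/70 to 130/75 | 80 to 105 (rise 25) | no | no | yes | present | absent |
| 120/70 to 120/70 | 80 to 101 (rise 21) | no | no | yes | present | absent |
| 120/70 to 120/70 | 80 to 100 (rise 20) | no | no | no | absent | absent |
| 120/70 to 120/70 | 60 to 85 (rise 25) | no | no | no | absent | absent |
| 120/70 to 120/70 | missing | no | no | not evaluated | absent | absent |
| 120/70 to 100/70 | 70 to 75 (rise 5) | yes | no | no | present | present |

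The first four rows are positive on C alone; in two of them pressure rose. The second and seventh rows have the same pressures and differ only in whether pulse was recorded, yet they are classed differently.

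**Direction.** The set satisfying A or B or C contains the set satisfying A or B. Adding C can increase the count or leave it unchanged. It cannot reduce it.

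**Size per subject.** If k of n subjects meet C but neither A nor B, the reported proportion exceeds the pressure-only proportion by k/n. At n = 35:

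- k = 1: 1/35 = 2.9 points
- k = 2: 2/35 = 5.7 points
- k = 3: 3/35 = 8.6 points

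Protocol Section 1.2.4 reports 2 deaths among the 35 parent-study subjects, which leaves at most 33 who could enter; 1/33 = 3.0 points. The share per subject grows as n falls. The documents give no value for k.

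**The case against.** The strongest reply is that the rule is deliberate. It was added as a definition, and the missing-pulse sentence shows that its authors meant pulse to be a separate route to a positive result. The documents offer no other standard for orthostatic hypotension against which a pulse-only case could be called a false positive. The study is descriptive with no hypotheses (SAP Section 4.1), and no decision is tied to this flag. Lying and standing values are collected, vital signs are summarized at each visit, and safety data go into subject listings, so a pressure-only classification could be recovered.

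Most of this stands, and it limits the importance of the point. It does not justify the label. If a broader orthostatic measure was intended, it should not be reported as hypotension without showing its components.

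A reader might infer more than the documents support:

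- *Any pulse rise above 20 bpm is enough.* It is not. The rate must also exceed 100 bpm, so 60 to 85 is not flagged.
- *Atrial fibrillation will often trigger the rule.* Protocol Section 1.2 lists it as a symptom, and Section 1.2.4 mentions fibrillation or flutter at the parent study's baseline. Neither gives a frequency, and nothing states how far two pulse readings would differ from irregularity alone.
- *By-visit percentages will be inflated.* The SAP defines the condition and implies evaluation at each visit, but it specifies no by-visit percentage table.
- *The reported rate will be wrong by a known amount.* Neither a pressure-only rate nor a pulse-only frequency is given, so no inflated rate can be derived.

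**Conclusion.** The point holds. Followed exactly, SAP Section 8.3 counts subjects as having orthostatic hypotension when pressure is unchanged or rises on standing, provided the pulse rises by more than 20 bpm and exceeds 100 bpm. It also classes the same pressures differently when pulse is missing.

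The direction is certain: upward or nil. The total size is unknown; it could be zero if no subject meets the pulse condition alone. The per-subject figure of about 2.9 points assumes that the summary is a proportion of subjects and that n is the full 35.

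This is a mislabelled descriptive safety count. It affects no hypothesis test, efficacy endpoint, mortality, hospitalization or adverse-event result. It is still worth correcting because the correction is cheap and loses no information.

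**What to change.** In SAP Section 8.3:

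- Define orthostatic hypotension by the systolic and diastolic conditions only, with their present thresholds.
- Tabulate the pulse condition as a separate row under an accurate name, such as orthostatic pulse increase, with a denominator of subjects who have both lying and standing pulse recorded.
- Remove the missing-pulse sentence, which then has no function.
- If the sponsor wants the combined measure for comparability with other outputs, keep it as an additional row that is not labelled hypotension.

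The cost is SAP wording and one or two table rows. No new data or procedures are needed.
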